### **VNS Therapy group:**

Volunteers who do not have gastrointestinal symptoms and undergoing VNS Therapy as part of treatment for focal or partial seizure will be recruited for the study. A total of 15 subjects will be recruited for the pilot study. This will help us determine if HRV is affected by VNS treatment.

Volunteers will be recruited from the IU Health Physicians Neurology clinic where the patients are being seen for a routine follow up clinical visit after the VNS placement.

1. Cervical neck electrodes used in this part of the study will include the multi electrode array (MEA) that are currently being used for a different protocol (IRB 1907095542). The MEA can be placed on either side of the neck over the area of the vagus nerve to record any electrical activity that might occur during the baseline period.
2. Two ECG electrodes are placed either one on each arm or on the chest for measurement of the electrocardiogram (ECG)

3. Three ECG electrodes are placed on the abdomen in a line parallel to the longitudinal axis of the stomach to record the electrogastrogram (EGG).

A onetime baseline recording will be made for 20 minutes after which the subject will be discharged from the study. There will be no follow up visit for these subjects in the pilot study.

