## **INVESTIGATIONAL PLAN**

Healthy human subjects ranging in age between 18 to 80 years and who are able to give informed consent are considered candidates for study. Pregnant subjects are excluded from study.

The consent may be administered by the study team either in person or virtually using RedCap platform.

A modality of therapy currently being utilized to treat focal or partial seizures that do not respond to seizure medications is called as VNS Therapy (Vagus Nerve Stimulation). This has been approved by FDA as an effective treatment for seizure disorders. Our aim is to study the HRV in patients undergoing this therapy as part of their regular mode of treatment. The specific aim is to measure the HRV in patients undergoing vagus nerve stimulation therapy.

[figure not shown]
During VNS treatment the stimulator is surgically implanted in the upper chest and stimulation electrodes are implanted in the left cervical vagus nerve.

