#### ABVN Phase 2 Outcome Measures/Endpoints

1. To measure the amplitude of vagal nerve compound action potentials in gastroparetic subjects with symptoms of nausea and vomiting with skin electrodes over right and left vagus nerve during ABVN stimulation and also during the vagal maneuvers phase
2. To measure respiratory changes in heart rate during ABVN and also during the vagal maneuvers phase.
3. To measure changes in the amplitude of the surface electrogastrogram during ABVN and also during the vagal maneuvers phase.
4. To measure the Heart rate variability(HRV), vagal nerve compound action potentials and electrogastrogram in subjects undergoing VNS Therapy for focal or partial seizures.
5. To measure the effect of ABVN stimulation on the gastric hormones in healthy and gastroparetic subjects.
6. To see the effect on the data if we change the regular ECG electrodes to MEA electrodes in the neck.
7. To see the effect of COVID 19 on HRV in healthy volunteers diagnosed with COVID-19

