#### Inclusion criteria for VNS Therapy subjects

1. Volunteers with no GI symptoms
2. Ages 18-80
3. Undergoing VNS Therapy as part of clinical treatment for focal or partial epilepsy or seizure
4. Willing to have MEA electrodes placed on the neck and bipolar electrodes placed on chest and stomach

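### The VNS recording fixes neither the side of the neck array nor the device's on and off periods, which limits what endpoint 4 can say about VNS

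*Protocol*

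**What the plan says.** The Investigational Plan describes the implant: "stimulation electrodes are implanted in the left cervical vagus nerve". Endpoint 4 in the Outcome Measures list is: "To measure the Heart rate variability(HRV), vagal nerve compound action potentials and electrogastrogram in subjects undergoing VNS Therapy for focal or partial seizures".

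The procedure is in the section on the VNS Therapy group. On neck electrodes it says: "The MEA can be placed on either side of the neck over the area of the vagus nerve". The stated purpose is to pick up whatever electrical activity appears in the baseline period. On size: "A total of 15 subjects will be recruited for the pilot study". On the recording: "A onetime baseline recording will be made for 20 minutes after which the subject will be discharged from the study". On any return: "There will be no follow up visit for these subjects in the pilot study". The same section gives the group's purpose as finding out whether VNS treatment alters HRV.

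The inclusion criteria for VNS subjects add only "Willing to have MEA electrodes placed on the neck and bipolar electrodes placed on chest and stomach", with no side named. None of these sections says whether the implanted device is on, off or cycling during the 20 minutes, and none describes a marker, log or synchronisation of its output.

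**The concern.** Two features of the recording bear on whether endpoint 4 can be linked to VNS.

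The first is side. The stimulated nerve is on the left. If the only array is on the right, the recording is taken over the other nerve, and a potential evoked locally by the device would not be expected there. If side varied between subjects, it would also add variation in CNAPs unrelated to VNS.

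The second is device state. A question about the effect of VNS needs periods with and without stimulation, or some other comparator. A single recording labelled baseline, with no identification of device output, supplies neither. This matters more than side, because it reaches HRV, which is the group's stated purpose, as well as CNAPs and EGG.

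Both are decisions about data acquisition. An analysis plan cannot add a side that was not recorded, and it can assign device state later only if the trace or the stored device settings allow it.

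**Working it through.** The plan gives no derivation for the 15 subjects and no figure to reproduce, so the check is a comparison of sections.

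**Side**
1. Stimulated nerve: left cervical vagus (Investigational Plan).
2. Recorded nerve in VNS subjects: either side, permissive wording (VNS Therapy group). The VNS inclusion criteria do not narrow it.
3. The same sentence appears in the Vagal Maneuver Group section for healthy volunteers. They have no left-sided implant, so side carries less meaning there, and their baseline precedes maneuvers. In the VNS group nothing follows the baseline. The text seems to have been carried over without adaptation.
4. In both Ear Stimulation Group sections, the protocol states outright that neck electrodes go on both sides. The VNS section does not.
5. In the gastroparetic Vagal Maneuver Group section, however, the bipolar electrodes are also allowed on either side, while endpoint 1 calls for electrodes over the right and the left nerve in that phase. So the protocol may use this phrase to mean both.
6. Result: the wording is ambiguous. Left only, right only and both would all comply.

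**Device state**
1. Recordings per subject: one of 20 minutes, with no follow-up visit.
2. Device status during it: not stated. Means of identifying it: none described.
3. The Data Analysis section compares a sham baseline with successive levels of ear stimulation. The VNS group has neither, so that analysis does not supply the missing contrast.
4. Result: no within-subject comparison of stimulated with unstimulated time is set up for any of the three measures.

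**Reach**

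| Gap | HRV | CNAP | EGG | Subjects affected |
|---|---|---|---|---|
| Side | no | yes | no | 0 to 15 (not determined by the text) |
| Device state | yes | yes | yes | 15 of 15 |

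The range 0 to 15 is simply the possible number recorded on the right alone. The protocol offers no basis for a narrower estimate.

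**The case against.** The strongest reply is that either side means both sides. The gastroparetic maneuver section, read with endpoint 1, supports this, and on that reading an array lies over the stimulated nerve in every VNS subject. A reader might infer that the plan deliberately records an arbitrary single side. The documents do not say so. What stands is that the sentence is permissive and a right-only recording would not breach it.

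A reader might also infer that stimulated and unstimulated signal will be averaged together. The protocol states no such rule, and segmentation could be set in an analysis plan that is not shown. What stands is that the protocol does not require the information such segmentation would need.

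Nor does the absence of a second visit make the problem beyond repair. Stimulus artefact in the trace, or the clinic's device settings, might reveal the timing afterwards. But nothing requires the settings to be captured or the artefact to be kept.

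The protocol cited for the array (IRB 1907095542) is not shown and may contain relevant procedures. Its title in Appendix 4 concerns gastric electrical stimulation, so nothing visible indicates that it covers VNS side or timing.

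Finally, this is a 15-subject pilot aimed mainly at HRV, which array side does not affect, and endpoint 4 promises measurement, not a device-evoked response. That is fair, and it limits the weight of the side point. It does not answer the device-state point, because the HRV aim is itself a question about the effect of VNS.

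**Conclusion.** The point holds as a cheap improvement to a small exploratory component. It does not undermine the trial.

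The side wording allows, but does not prescribe, recording over the unstimulated nerve alone, and this affects only the CNAP part of endpoint 4. The unmarked device state affects HRV, CNAPs and EGG in all 15 subjects: as written, there is no within-subject contrast for the HRV aim, and a CNAP can be attributed to stimulation only where artefact happens to show it. It would go too far to say that the CNAP data will be uninterpretable, or that a known share of subjects will be recorded on the wrong side.

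The conclusion assumes that implants are on the left, as the protocol states, and that the unseen array protocol does not already settle side and timing. The documents do not describe the device's cycle. If a subject's 20 minutes hold only one device state, marking will show that, but it cannot create a contrast for that subject.

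**What to change.** In the VNS Therapy group section:

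- Require the array over the implanted (left) side in every VNS subject. Allow a second array on the right as an optional within-subject comparison.
- Time-stamp the device's on and off periods during the recording, from the stimulus artefact and supported by the device settings, without changing therapy settings.
- Report HRV, CNAP and EGG separately by on and off period.

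The cost is a few sentences of protocol text and annotation of a recording already planned. No extra subjects or visits are needed. The downside is more stimulus artefact in left-sided recordings, which must be blanked or flagged by a rule set in advance.

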#### **Gastroparetic subjects without implanted gastric stimulators;**

Gastroparetic subjects ranging in age between 18 to 80 years and who are able to give informed consent are considered candidates for study. Pregnant subjects are excluded from study.

Approximately 40 gastroparesis subjects will be recruited for this new phase of the study.

#### **Inclusion Criteria**

- Gastroparesis subjects with a confirmed diagnosis of gastroparesis from a GI physician
- Have a formal diagnosis of gastroparesis or are seeing the GI physician for symptoms related to gastroparesis
- Aged 18-80 years
- Willing to have electrodes placed in the external ear (ABVN arm)
- Willing to perform vagal activity maneuver (Vagal arm)
- Willing to have 1 tablespoon (15 ml) of blood drawn at 3 time points

#### **Exclusion Criteria**

- Unable to provide consent
- Pregnant females
- Prisoners

#### **Study Procedures:**

Gastroparesis subjects who meet the inclusion and exclusion criteria will be enrolled in the study.

#### **VAGAL MANEUVER GROUP:**

Gastroparetic subjects will be recruited initially to see the effect of these maneuvers on the vagal activity.

A total of 40 gastroparetic subjects will be recruited. These subjects can be the same subjects that enroll in the ear stimulation group of the study or can be entirely new subjects.

At the beginning of the study, a baseline recording of 10- 20 minutes will be made following which the maneuvers will be conducted. Cervical neck electrodes used in this

part of the study include the bipolar EKG electrodes. The bipolar electrodes can be placed on either side of the neck over the area of the vagus nerve to record any electrical activity that might occur during the baseline period. Baseline ECG and EGG recordings are also performed during this interval by placing the electrodes over the chest and over the stomach area for ECG and EGG recordings.

After 10 seconds of each maneuver, another 10-20 minutes of recording will be made before doing the next maneuver.

For the eating maneuver, there is no time restriction and the subject will drink it as per their capacity.

We will include the following maneuvers:

Cough; Each subject will be asked to generate approximately 6 to 8 forceful and sustained coughs for 10 seconds.

Cold stimulus to face: We propose to place a washcloth soaked in ice water on each subject's face for about 10 seconds. This creates a physiological response to a person being submerged in cold water (Diver's Reflex)

Carotid Massage: This technique is performed with the subject's neck in an extended position, the head turned away from the side being massaged. Only one side is massaged at a time. Pressure is applied underneath the angle of the jaw in a gentle circular motion for about 10 seconds. The subject is monitored throughout.

Gagging: A tongue depressor is briefly inserted into the subject's mouth for about 10 seconds touching the back of the throat, which causes the person to reflexively gag. The gag reflex stimulates the vagus nerve.

Valsalva maneuver: The subject is instructed to bear down as if they were having a bowel movement. The subject is asked to blow through a mouthpiece that is hooked to a device used in clinical spirometry until the pressure reaches 10mmHg. Alternatively, we can have the subject blow through the barrel of a 10 ml syringe for 10 seconds. This maneuver increases intrathoracic pressure and stimulates the vagus nerve.

Eating: Subjects will be asked to drink water or/ and Ensure Original that has 220 calories after fasting overnight to see that effect on vagal activity during eating. The subjects take their time to drink the water or ensure and the time to finish the drink is noted.

All the maneuvers described above will be conducted for duration of 10 seconds each except wherever stated otherwise and the recordings will be made for duration of 5-10 minutes after each maneuver. If it is not possible to do all the maneuvers in one visit, then

they will be conducted over two or more visits. Sometimes not all maneuvers will be conducted, and this will depend on the discretion of the investigator.

**EAR STIMULATION GROUP:**

This is a onetime visit only that involves baseline and test procedures.

1. Two MRI compatible electrodes will be placed in the auricle of the left ear, fixed by a plastic armature that wraps around the ear. The leads from the electrodes are connected to a stimulator.
2. A pneumatic belt may be placed around the lower thorax. Pneumatic tubes connect this belt to a pressure transducer that in turn sends signal to a laptop-controlled device that acquires the signals.
3. Two ECG electrodes are placed on both sides of the neck overlying the area near the carotid artery where the vagus nerve is superficial. This is to measure the vagal action potentials in the neck.
4. Two ECG electrodes are placed one on each arm and one on the chest for measurement of the electrocardiogram (ECG)
5. Three ECG electrodes are placed on the abdomen in a line parallel to the longitudinal axis of the stomach to record the electrogastrogram (EGG).

Electrical stimulation of the electrodes placed in the ear is provided by a current-constant stimulator. The stimuli consist of rectangular pulses with 450  $\mu$ s pulse width, delivered at 30 Hz, and pulse train duration of 0.5 seconds. Stimulation is gated, with 0.5-second delay, after peak inhalation (i.e., during exhalation) or after peak exhalation (i.e., during inhalation).

Baseline procedure:

A butterfly catheter is inserted under aseptic conditions into a peripheral vein. Fifteen ml (1 tablespoon) of blood is withdrawn and placed on ice. After this the baseline recording will be started as described below.

During the baseline recording the stimulating electrodes are placed in the auricle of the subject but no current is delivered. Cervical neck electrodes are placed over the right and left vagus nerve to record any electrical activity that might occur during the baseline period. Baseline ECG and EGG recordings are also performed during this interval.

Test procedure:

Stimuli consisting of rectangular pulses with 450  $\mu$ s pulse width, delivered at 30 Hz, and pulse train duration of 0.5 seconds are then delivered to the subject. Current intensity is set to achieve moderate to strong (but not painful) sensation, and pulse frequency/duration is set following pilot testing to achieve a subjectively comfortable stimulus sensation. This is 4/10 and is designated “100 per cent.” The current amplitude

**PI: [name] Effect of Electrical Stimulation of the Auricular Branch of the Vagus Nerve on Cervical Vagus Nerve Compound Action Potentials**

is then increased again by 10 per cent and ABVN is applied again for 60 seconds. This sequence is repeated until the “100 percent” level (4/10) is reached. These stimuli are delivered during expiratory phase of respiration as investigations have shown this to be most effective in producing vagal stimulation (8).

Once the target stimulus intensity has been achieved, stimuli are delivered during the expiratory phase for a total of two minutes. Another 15 ml (1 tablespoon) of blood will be collected 20 minutes after stopping the stimulus.

The subject will be allowed to keep on resting and 20 minutes after the second blood draw, another 15 ml (1 tablespoon) of blood will be drawn. This is the final draw. The catheter will then be withdrawn

The subject will then undergo stimulation at the “100 percent” designated level for 2 minutes and a 5-minute post stimulation recording may be made. This will be followed by another 2-minute stimulation followed by 5 minute of post stimulation recording.

At the end of the 5-minute post stimulation recording. The subject will be allowed to go home

ECG and EGG recordings will be continued during auricular branch vagal nerve stimulation.

If the blood collection is not possible due to any reasons the subjects will still go ahead with the auricular branch stimulation of 2 minutes and 5 minutes recording made after that.

**Risks:**

There is no pain associated with this protocol. Prior to the study, subjects are asked at what threshold they experience discomfort and subsequent stimuli are delivered below the discomfort threshold. There is a small possibility of slight and temporary discomfort at the site where the electrodes are placed. Potential vaso-vagal reactions to stimulation resulting in dizziness or light-headedness will be promptly recognized and treated by a study physician or clinically trained personnel with prompt removal of the electrodes or other vagal stimulus and repositioning the subject into a supine position. In some subjects, the experience of electrical stimulation may cause anxiety in which case the electrodes will be removed. Subjects will be required to remain under supervision until all symptoms subside. A study physician will be available at all times to discuss the study with subjects should they become concerned.

The electrical stimulation procedure is without significant safety concerns. The electrical stimulator, checked by Biomedical Engineering, has a current limiter preventing harmful stimulation levels. Further, during the electrical stimulation, we will be closely

**PI: [name] Effect of Electrical Stimulation of the Auricular Branch of the Vagus Nerve on Cervical Vagus Nerve Compound Action Potentials**

monitoring that the current received by the subject is well tolerated. Throughout the measurement sessions, participants will be repeatedly asked if they are well and comfortable. Should the subject feel any discomfort he or she will be advised to let the researcher know and the study will be immediately interrupted/terminated.

There may be a risk of transient ischemic attack (TIA) or mini stroke during the carotid massage maneuver.

The patient experiences some pain during venipuncture. An indwelling catheter is used to decrease the discomfort of multiple venipuncture. The procedure is performed using aseptic technique to minimize the risk of infection. Pressure and a bandage are applied over the venipuncture site to minimize the risk of bleeding.

There is no additional risk as part of the recording for VNS Therapy subjects that are research related.

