#### Inclusion Criteria

- Healthy volunteers with no gastric symptoms or conditions (except due to COVID 19)
- Aged 18-80 years
- Willing to have electrodes placed in the external ear (ABVN arm)
- Willing to perform vagal activity maneuver (Vagal arm)
- Willing to have 1 tablespoon (15 ml) of blood drawn at 3 time points

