#### Exclusion Criteria

- Unable to provide consent
- Having gastric motility issues (not due to COVID 19) as determined by the PI or Sub I
- Taking medications affecting gastric motility
- Pregnant females
- Prisoners

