#### **Study Procedures:**

Healthy volunteers who meet the inclusion and exclusion criteria will be enrolled in the study. They will complete a Health History questionnaire that asks in detail about their health history along with any medications that they may be on. If they have been diagnosed with COVID 19 then they will be asked to complete another questionnaire about their symptoms. If they meet all the requirements for the study, then they will do the following

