#### **VAGAL MANEUVER GROUP:**

Healthy volunteers will be recruited initially to see the effect of these maneuvers on the vagal activity.

A total of 10 healthy volunteers will be recruited. These subjects can be the same subjects that enroll in the ear stimulation group of the study or can be entirely new subjects.

At the beginning of the study, a baseline recording of 10- 20 minutes will be made following which the maneuvers will be conducted. Cervical neck electrodes used in this part of the study will include the multi electrode array (MEA) that are currently being used for a different protocol (IRB 1907095542). The MEA can be placed on either side of the neck over the area of the vagus nerve to record any electrical activity that might occur during the baseline period. Baseline ECG and EGG recordings are also performed during this interval by placing the electrodes over the chest and over the stomach area for ECG and EGG recordings.

In a previous protocol (IRB 1809685671) healthy volunteers have already been recruited using the bipolar ECG electrodes for the vagal nerve recording in the neck, hence a total of 10 healthy volunteers to be recruited using the MEA electrodes for comparison of data.

After 10 seconds of each maneuver, another 10-20 minutes of recording will be made before doing the next maneuver.

For the eating maneuver, there is no time restriction and the subject will drink it as per their capacity.

We will include the following maneuvers:

Cough; Each subject will be asked to generate approximately 6 to 8 forceful and sustained coughs for 10 seconds.

Cold stimulus to face: We propose to place a washcloth soaked in ice water on each subject's face for about 10 seconds. This creates a physiological response to a person being submerged in cold water (Diver's Reflex)

**Carotid Massage:** This technique is performed with the subject's neck in an extended position, the head turned away from the side being massaged. Only one side is massaged at a time. Pressure is applied underneath the angle of the jaw in a gentle circular motion for about 10 seconds. The subject is monitored throughout.

**Gagging:** A tongue depressor is briefly inserted into the subject's mouth for about 10 seconds touching the back of the throat, which causes the person to reflexively gag. The gag reflex stimulates the vagus nerve.

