**Valsalva maneuver:** The subject is instructed to bear down as if they were having a bowel movement. The subject is asked to blow through a mouthpiece that is hooked to a device used in clinical spirometry until the pressure reaches 10mmHg. Alternatively, we can have the subject blow through the barrel of a 10 ml syringe for 10 seconds. This maneuver increases intrathoracic pressure and stimulates the vagus nerve.

**Eating:** Subjects will be asked to drink water or/ and Ensure Original that has 220 calories after fasting overnight to see the effect on vagal activity during eating. The subjects take their time to drink the water or ensure and the time to finish the drink is noted.

All the maneuvers described above will be conducted for duration of 10 seconds each except wherever stated otherwise and the recordings will be made for duration of 5-10 minutes after each maneuver. If it is not possible to do all the maneuvers in one visit, then they will be conducted over two visits. Sometimes not all maneuvers will be conducted, and this will depend on the discretion of the investigator.

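### The protocol names TIA or mini stroke as a risk of carotid massage but never says who should not be massaged, and it describes no health history form for gastroparetic subjects

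*Protocol*

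**What the plan says.** The Risks section says of one maneuver: "There may be a risk of transient ischemic attack (TIA) or mini stroke during the carotid massage maneuver". No preventive step accompanies that sentence.

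Carotid massage is one of six maneuvers in both Vagal Maneuver Group sections, with 10 healthy volunteers in one and 40 gastroparetic subjects in the other. The technique is limited: "Only one side is massaged at a time", with gentle pressure for roughly 10 seconds and the subject monitored. Both sections add: "Sometimes not all maneuvers will be conducted, and this will depend on the discretion of the investigator".

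Eligibility is as follows.

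- **Healthy volunteers.** Health is described in gastric terms: "Healthy volunteers with no gastric symptoms or conditions (except due to COVID 19". The exclusions are inability to consent, motility problems ("Having gastric motility issues (not due to COVID 19) as determined by the PI or Sub I"), drugs that affect motility, pregnancy and being a prisoner. The Study Procedures add a history form: "They will complete a Health History questionnaire that asks in detail about their health history along with any medications that they may be on".
- **Gastroparetic subjects.** The only criterion about maneuvers is willingness: "Willing to perform vagal activity maneuver (Vagal arm". There are three exclusions: "Unable to provide consent", pregnancy and being a prisoner. The Study Procedures for this cohort say only that subjects who meet the criteria are enrolled, and mention no history form.

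**The concern.** The protocol recognises a serious neurological hazard but does not carry it into eligibility or into the procedure. Elsewhere in the Risks section a hazard comes with an action: vasovagal reactions with removing the stimulus and laying the subject flat, anxiety with removing the electrodes, venipuncture with a catheter and aseptic technique. The gravest one named has no matching step.

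The screening is also the wrong way round. The cohort presumed healthy completes a detailed history. The patient cohort, four times as large and admitted up to age 80, is not described as doing so.

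Participant safety is at stake. A person who has already had the event that the protocol warns of can be enrolled and massaged, unless an investigator knows of it and chooses to skip the maneuver. No endpoint or analysis is affected.

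**Working it through.** The protocol gives no figure to reproduce. The check is a count of criteria and a comparison of the two cohorts.

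**1. Criteria that address the named risk**

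| Cohort | Inclusion | Exclusion | Concerning TIA, stroke or carotid disease |
|---|---|---|---|
| Healthy volunteers | 5 | 5 | 0 |
| Gastroparetic subjects | 6 | 3 | 0 |

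Total: 5 + 5 + 6 + 3 = 19 criteria, of which 0 address the risk. Among the exclusion criteria alone, where such a rule would normally stand, it is 0 of 5 + 3 = 8.

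**2. Subjects exposed**

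From the two Vagal Maneuver Group sections: 10 + 40 = 50. This is the planned maximum, because maneuvers may be omitted. It is not a hard ceiling, since the introduction to the gastroparetic cohort calls its 40 approximate. The VNS Therapy group is not counted because it has only a baseline recording.

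**3. Is the information available to apply a rule?**

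- Healthy volunteers: yes. History and medications are collected before procedures, and the form feeds the decision on whether the requirements are met. Only the written rule is missing.
- Gastroparetic subjects: not by any step in the text. The Health History questionnaire appears once in the protocol, for healthy volunteers. Both the rule and the described source of information are missing.

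**4. What each existing safeguard does**

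| Safeguard | Where | Says whom to spare? |
|---|---|---|
| One side, gentle, brief, monitored | Vagal Maneuver Group, both cohorts | No; it limits the exposure |
| Discretion to omit maneuvers | Vagal Maneuver Group, both cohorts | No; it needs information and states no ground |
| Treatment, supervision, stopping for discomfort | Risks | No; it responds once something happens |
| Review after the first subject, then monthly | Data Safety Monitoring | No; it is oversight |
| Withdrawal by the investigator for safety | Study withdrawal/ Discontinuation | No; general |

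**5. Cost of the fix**

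The protocol gives no share of subjects with a relevant history. On an assumed range of 2% to 10%: 0.02 × 50 = 1 and 0.10 × 50 = 5 massage recordings lost out of 50.

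**The case against.** The strongest reply is that the protocol is better protected than a bare count suggests. The massage is brief, gentle and one-sided. A study physician is available throughout, subjects are asked repeatedly how they feel, adverse events are reviewed monthly with an independent physician, and investigators may omit any maneuver. Healthy volunteers give a full history, and a person with a previous stroke would hardly pass as healthy. Gastroparetic subjects are under a GI physician, so some clinical information exists. The protocol does not say that previous TIA or stroke raises the risk from massage; that link is a clinical premise. The count of 19 includes items that could never bear on this risk, such as age and willingness to give blood. Finally, consent and appendix pages are not available and may hold further precautions.

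Much of this stands. The gap is small for the 10 healthy volunteers. The count of 8 exclusions is the fairer denominator, though the result is still zero. The premise about previous events is a clinical assumption and should be labelled as one. Nothing can be inferred about actual practice at the site.

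It does not close the gap for the 40 gastroparetic subjects. Discretion works only with information, and the protocol requires no vascular history to be taken or passed to the person doing the massage. The GI physician's role in the criteria is to establish gastroparesis. Monitoring and stopping rules act after exposure has begun. Precautions in a consent form would not supply a missing rule in the protocol, and eligibility is not something to leave to a statistical analysis plan.

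**Conclusion.** The concern holds. The protocol names a serious risk of carotid massage and contains no criterion, in either maneuver cohort, that says who should not receive it. For the gastroparetic cohort it also describes no history form with which such a rule could be applied. Up to 50 planned subjects are affected, with the weight on the 40 gastroparetic subjects. The size of the harm cannot be estimated, because the protocol gives no event rate.

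The conclusion rests on the eligibility and procedure text available. It also takes as a clinical assumption that previous TIA, previous stroke or known carotid disease is a sensible ground for withholding the massage; the study physicians should confirm or extend that list. It should be corrected, and correcting it is cheap.

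**What to change.** 1. Under Carotid Massage in both Vagal Maneuver Group sections, add: *Not performed in subjects with a history of TIA or stroke or known carotid disease, or with any further condition listed by the study physicians; these subjects may do the other five maneuvers.* The physicians' list should be fixed in writing before the first massage, so that the clause does not simply restore open discretion.
2. In the Study Procedures for gastroparetic subjects, require the existing Health History questionnaire before any maneuver.
3. In both cohorts, have the completed questionnaire checked against this restriction before the massage.

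Placing the restriction at the procedure, rather than in the general exclusion list, keeps affected subjects in the study. It suits a design that already accepts incomplete sets of maneuvers. The cost is one sentence in two places, one existing form used in a second cohort, a short check in both, and slightly fewer massage recordings.
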